2.8 DATA AND POWER ANALYSES

2.8.1 Primary Endpoint Data Analyses:

Baseline demographic and clinical data of participants will be summarized using means (with standard deviations) and medians (with inter-quartile ranges) for continuous variables, and counts and percentages for discrete variables, stratified by treatment group. Differences among groups (to examine the randomization effectiveness), will be assessed by t-tests, or by Fisher's exact test for discrete data, recognizing the limited power of our small trial.

Repeated measures linear mixed models will be used to evaluate differences of immunological parameters (continuous variables) that comprise the primary, and most second endpoints. These models will track the changes over time as well as allow for missing observations, which should be minimal. In general, analyses will follow intention to treat principles, with the last observed outcome over all time points being used as the primary measure for a given variable.

The sample size of 18 subjects for this clinical trial is based on exposing a minimum number of patients to potential risks of the experimental therapy, while having the potential to obtain useful information. Given that this trial is unprecedented, it is impossible to use preliminary data to definitively derive power analyses. Indeed, an important purpose of this study is to generate credible and relevant preliminary data in this population to power subsequent larger trials. Trials to detect clinical efficacy (e.g., change in pulmonary function tests, reductions in acute exacerbations, etc.) will almost certainly require treatment of many subjects over prolonged periods.

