With these limitations in mind, we can assume belimumab effects in COPD patients are similar to those among patients with SLE. Thus, we can expect to see reductions of anti-GRP78 autoantibody concentrations by ~30%, in addition to ~50% reductions of several circulating B-cell subpopulations, by or after approximately 6 months of therapy. With respect to the primary endpoint (reduction of anti-GRP78 IgG): If the true difference in the experimental and control means is 30%, with standard deviations that are two–thirds of this (20%), we will need to study 12 experimental subjects and 6 control subjects to reject the null hypothesis that the population means of the experimental and control groups are equal, with probability (power) 0.8. The Type I error probability associated with this test of the null hypothesis is 0.05.

The 2:1 experimental arm: control enrollment will increase the amount of data regarding effects and safety of this drug in COPD patients, and only increases the necessary subject number to reach 80% power by two, compared to 1:1 enrollment.

2.8.2 Secondary Endpoint Data Analyses: Analyses will again follow intention to treat principles, with the last observed outcome over all time points being used as the primary measure for a given variable. Multiple imputation will be used based on subject characteristics to assess the obvious issues with last observations carried forward in these analyses. Trajectories over time, for a given patient and outcome measure, will be displayed via line graphs, and assessments conducted using linear mixed models on the repeated time points. Comparisons between the treatment arms of the polysaccharide binding assay concentrations and B-cell parameters at various time points will be made using repeated measures techniques. Transformations of these tests may be needed, such as velocities, if many individuals are unable to complete the entire treatment protocol. The proportion of subjects with adverse events and the count of adverse events per subject will be compared by treatment using Fisher's exact test and the exact Poisson tests, respectively.

2.8.3 Interim Analysis: Since the primary endpoint of this trial is a laboratory test and surrogate biomarker, rather than a clinical outcome parameter, and the subject number is small, no interim analysis will be conducted for efficacy.

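### The imputation check on last observation names neither treatment arm nor earlier outcomes and omits the primary endpoint; the mixed model already planned should govern

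*Combined protocol and SAP*

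**What the plan says.** Section 2.8.1 (primary endpoint) and Section 2.8.2 (secondary endpoints) both state an intention-to-treat analysis "with the last observed outcome over all time points being used as the primary measure for a given variable". Both sections also plan linear mixed models on the repeated measurements, and Section 2.8.1 notes that these tolerate missing visits. Neither section says which result governs if the two differ.

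Section 2.8.2 alone adds a check: "Multiple imputation will be used based on subject characteristics to assess the obvious issues with last observations carried forward in these analyses". It gives no list of imputation variables, no number of imputations and no missing-data assumption. Section 2.8.1 has no corresponding check for the primary endpoint.

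Section 2.8.2 then allows a change of outcome: "Transformations of these tests may be needed, such as velocities, if many individuals are unable to complete the entire treatment protocol". It does not define velocity, how many non-completers count as many, or who decides and when.

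On the amount of missing data, Section 2.8.1 expects very little. The synopsis (Planned Sample Size) randomizes 25 to reach 18 because of early withdrawals.

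**The concern.** The plan gives its main role to a measure whose weaknesses it admits, so the check on that measure has to be sound. Read plainly, subject characteristics are descriptors such as age or smoking history, not randomized arm or post-baseline assay results. An imputation model without arm fills the gaps in both groups from one common distribution. The completed data then contain less treatment difference than the observed data, and the check is biased toward no effect.

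Two features of this trial make that matter.

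- **Host-defence antibodies.** The hypothesis for pneumococcal antibodies is that belimumab lowers them very little (Sections 1.2 and 2.9.2). If there is a real loss, a check biased toward no difference would understate it.
- **Informative drop-out.** Section 5.6.4 removes subjects whose exacerbations need added lung medication or hospitalization. Section 2.7.1 reports that anti-GRP78 readings tend to rise as lung disease worsens. For the primary endpoint, missingness may therefore be related to the outcome, yet no check is planned there.

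**Working it through.** **Inputs from Section 2.8.1.** The difference in means: "If the true difference in the experimental and control means is 30" percent. The SD and group sizes: "of this (20%), we will need to study 12 experimental subjects and 6 control subjects to reject the null hypothesis". The power: "population means of the experimental and control groups are equal, with probability (power) 0.8". The error rate: "The Type I error probability associated with this test of the null hypothesis is 0.05"; sidedness is not stated and is taken as two-sided.

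**The plan's own figure.** The standard error is 20 × √(1/12 + 1/6) = 10, so the noncentrality is 30/10 = 3.0 on 16 degrees of freedom. The two-sided t-test has power 0.804, which agrees with the plan. This calculation belongs to the primary endpoint. It is used below only as a scale, because the plan gives no SD for any secondary endpoint.

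**Effect of omitting arm.** Let f be the share missing at the final visit, equal in both arms and completely at random. Let m be the common mean of the imputed values. The completed mean in each arm is (1 − f) × arm mean + f × m. The f × m term cancels on subtraction, so the expected difference is (1 − f) × true difference.

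| Missing share f | True 30 becomes | True 50 becomes |
|---|---|---|
| 5% (assumed, for very little missing) | 28.5 | 47.5 |
| 10% | 27.0 | 45.0 |
| 20% | 24.0 | 40.0 |
| 28% (7/25, upper assumption) | 21.6 | 36.0 |

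The 50 column corresponds to the B-cell expectation in Section 2.8.1: "50% reductions of several circulating B-cell subpopulations".

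**Simulation check.** Assumptions not in the documents: 25 randomized as 17:8; true difference 30, SD 20; one baseline characteristic with R² 0.10; one earlier value of the outcome correlated 0.6 with the final one, carrying half the effect; 20 imputations combined by Rubin's rules; about 1,500 runs per cell. The last column makes drop-out depend on the earlier value, at a baseline rate of 28%.

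| Imputation model | 10% random | 20% random | 28% random | 28%, outcome-dependent |
|---|---|---|---|---|
| Characteristics only | 26.8 | 23.7 | 21.1 | 18.2 |
| Plus earlier outcome, no arm | 28.3 | 26.0 | 24.2 | 22.5 |
| Plus arm | 29.8 | 29.5 | 30.2 | 28.6 |
| Plus arm and earlier outcome | 30.2 | 30.1 | 30.3 | 30.5 |

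At 28% missing at random, power in the four rows is 0.33, 0.53, 0.73 and 0.78. Adding arm removes nearly all of the bias. Adding the earlier outcome removes the small remainder when drop-out depends on it, and gains roughly 3 to 9 points of power.

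**The case against.** The strongest reply is that the wording does not exclude arm or earlier values. A statistician could include both and remain within the plan. That is correct. A reader might infer that the plan imputes from baseline characteristics and nothing else, and therefore will shrink the effect. The documents do not say so: the shrinkage is conditional on arm being omitted.

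A second reply is that the imputation is a sensitivity analysis for secondary endpoints, and that the planned mixed models use all observed visits without it. This also stands, and it limits the damage. It does not settle the matter, because the text still calls the last observed value the primary measure and does not rank the mixed model against it.

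Third, the 28% may be too high. Withdrawn subjects may have post-baseline values, and the documents do not say whether all 25 or only 18 are analysed. Section 2.8.1 expects few gaps, and Section 2.9.1 cites near-complete retention in earlier studies at the centre. A fall from 30 to about 21 should therefore not be read as the expected bias of a planned analysis. It combines primary-endpoint figures with an upper-bound missing share, for a check that the plan offers only on secondary endpoints.

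On velocities, a reader might infer that they too shrink the effect, or that early leavers' slopes are about 66 times noisier than completers' (sums of squares of visit times 32.8 for months 0, 1, 3, 5, 7 against 0.5 for months 0, 1). The documents support neither reading. Nothing links velocities to attenuation, and the ratio assumes unweighted slopes fitted subject by subject, which the plan does not specify. There is also a trigger of a kind, non-completion, although it has no number.

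**Conclusion.** The concern holds as a gap in specification with a conditional bias. The only stated check on an admittedly weak main measure has an open imputation model and does not reach the primary endpoint. If arm is omitted, the check is pulled toward no difference by about the missing share: 30 becomes 28.5, 27, 24 or 21.6 at 5%, 10%, 20% or 28% missing. This assumes an equal missing share in both arms, completely at random. With outcome-dependent drop-out the simulated figure at the 28% baseline rate is 18.2, under the stated simulation assumptions. A check with that bias could not validate the last-observation result.

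Arm is the variable that matters most. Earlier outcome values are worth including for precision and for outcome-dependent drop-out, but omitting them while keeping arm does little harm (30.2 and 28.6 against a true 30). The velocity option is a separate and minor matter of analyst discretion.

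**What to change.** 1. State in Sections 2.8.1 and 2.8.2 that the repeated-measures mixed model on all observed visits is the governing analysis for the primary and continuous secondary endpoints. Keep the last observed value as a sensitivity analysis only.
2. If multiple imputation is kept, list its variables: treatment arm, the baseline value and all observed earlier values of the same outcome, plus any chosen characteristics. Apply it to the primary endpoint as well.
3. Delete the velocity option, or define velocity and set a numeric non-completion trigger, both fixed before unblinding.

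The cost is a few sentences of SAP text. No new data, visits or assays are needed, because the immunological assays are already scheduled at baseline and months 1, 3, 5 and 7.

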Funding Source:	GlaxoSmithKline (GSK)
Study Rationale:	This is intended to be an initial "proof-of-concept" study to show feasibility, validate assays and approaches, and explore dosing and safety of belimumab in pulmonary COPD patients who have clinically relevant (and quantifiable) autoimmune responses.
Study Objectives:	The primary goal of clinical trial is to determine effects of belimumab on levels of autoantibodies against glucose regulated protein 78 (GRP78) among patients with pulmonary COPD attributable to cigarette smoking.
Study Hypothesis:	Our study hypothesis is that belimumab treatment will safely reduce circulating levels of autoantibodies that are associated with COPD, and comorbidities of this lung disease, including atherosclerosis.

Study Aims:	 Specific Aim 1: To conduct a double-blind, Phase II trial, in which 18 former smokers with COPD and circulating anti-GRP78 autoantibody levels >mean normal values (by ELISA), will be randomized 2:1 to belimumab vs. placebo. Subjects will receive 8 infusions of either belimumab or placebo over a 6 month interval. Plasma anti-GRP78 antibodies will be measured pre-treatment, and at 1, 3, 5, and 7 months. We hypothesize belimumab therapy will more effectively reduce anti-GRP78 IgG autoantibodies, the primary endpoint of this trial, compared to placebo. Specific Aim 2: To determine effects of the belimumab therapy on secondary endpoints (at the times detailed for Aim 1) that include levels of pneumococcal-binding antibodies (by ELISA), circulating B-cell numbers and phenotypes (by flow cytometry), and the rate and severity of adverse events (AE) at any time during treatment. We hypothesize belimumab will have dose-related effects on B-cell numbers and their differentiation, while minimally reducing host defense antibodies, and will also have an acceptable AE profile.
Study Design:	Following baseline screening assessments, patients that meet all inclusion/exclusion criteria will be randomly assigned to receive one of the following treatments in a ratio of 2:1:
	1.) Arm 1: Belimumab (n = 12). Subjects randomized to the experimental treatment arm will receive i.v. administrations of belimumab (10 mg/kg), consisting of three "loading" doses, two weeks apart, followed by five (5) more monthly infusions. The final dose is administered at month 6 with final assessment at month 7 and a safety visit at month 10.

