2.7.2. Secondary End-Points

Specific Aim 2 Endpoints: The secondary endpoints of this trial are: 1.) treatment effects on concentrations of pneumococcal polysaccharide-binding antibodies by ELISA^{33,36} 2.) treatment effects on absolute numbers and phenotypes of circulating B-cells by flow cytometry,⁸ and 3.) Adverse event comparisons.

Secondary endpoint #1. (anti-pneumococcal antibodies) and #2. (B-cells) will be assessed among blood specimens obtained prior to treatment, and at 1, 3, 5, and 7 months after treatment starts. Secondary endpoint #3 (AE) will be assessed at each clinic visit, telephone encounter and in communications initiated by subjects or study personnel at any other interval.

a.) Pneumococcal polysaccharide-binding antibody concentrations in plasma will be measured pre-treatment, and compared to results at the aforementioned intervals after treatment started. The ELISA methodology is straightforward, highly standardized, and fully detailed previously.³⁶

b.) B-cell numbers and phenotypes will be assessed at the same time-points. Method-ologies are also well established and have been previously detailed.⁸ In brief, B-cells will be stained with panels of fluorochrome-conjugated monoclonal antibodies and characterized by flow cytometry. B-lymphocytes will be identified as CD3⁻/CD14⁻/CD16⁻/CD19⁺ cells, and further stratified for comparisons as transitional (IgD⁺/CD38⁺⁺), IgM⁺ IgA⁻ IgG⁻ switched memory (IgD⁺/CD27⁺), IgG⁺ switched memory (IgD⁻/CD27^{+/-}), and plasmablasts (CD19^{lo/+}, CD20⁻, CD38⁺⁺, IgD⁻, CD27⁺⁺).⁸

c.) Adverse Events: The NCI Common Toxicity Criteria Scale will be used to define grades (severity) of adverse events and toxicities. An adverse event is defined as any untoward medical occurrence in a subject, regardless of its relationship to these treatments. Toxicity is an adverse event with a direct relationship to the study drug. All toxicities are adverse events, but not all adverse events are toxicities. Case report forms (CRF) will require responses to all adverse events (and negatives), with a particular focus on allergic reactions, infections (including location and organism), and neuropsychiatric symptoms. Recording adverse events in pre-specified checklists (and free text entries) in all subjects will guard against unintended bias.

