2.9.2 Specific Aim 2 (Secondary Endpoints) Anticipated Results and Pitfalls

Specific Aim 2 Anticipated Results:

a.) **Pneumococcal polysaccharide-binding antibody concentrations**: Based on results of analogous studies that examined belimumab effects in other populations (primarily SLE patients), we anticipate the experimental treatment will have only modest effects on concentrations of these important host defense immunoglobulins. Proving these antibodies are also minimally, if at all, affected in COPD patients (a novel trial population) is an important element of this pilot study. [name] is an expert with these types of assays and no technical problems are anticipated.

b.) B-cell Effects: Again, based on analogous literature in SLE populations, we anticipate a gradual shift in circulating B-cell phenotypes among the experimental treatment subjects, particularly those at the higher doses. In particular, we anticipate increases in proportions of less differentiated lymphocytes and corresponding decrements of more differentiated phenotypes. [name] is also experienced with these assays and no technical problems are anticipated.

c.) Adverse Events: Based on multiple studies involving thousands of patients treated with analogous regimens, we anticipate high-grade adverse events will not be significantly more frequent among experimental arm subjects, and the experimental regimen will have an acceptable risk:benefit ratio.^{33,34,37} Examining the safety of belimumab in this potentially high-risk population is a critical aspect of our small and conservatively biased pilot trial. It is conceivable this study will show that even carefully selected and closely observed COPD patients cannot tolerate any immune

suppression, even relatively benign belimumab. Even if so, these negative results (albeit disappointing) will be highly valuable, given the increasing interest (and seemingly increasing amount of supportive data and rationale) for therapeutic targeting of the autoimmune responses in these diseases.^{9,10}

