Note: An AE can therefore be any unfavorable and unintended sign (including an abnormal laboratory finding), symptom, or disease (new or exacerbated) temporally associated with the use of a medicinal product. For marketed medicinal products, this also includes failure to produce expected benefits (i.e., lack of efficacy), abuse or misuse.

Events meeting the definition of an AE include:

- Exacerbation of a chronic or intermittent pre-existing condition including either an increase in frequency and/or intensity of the condition
- New conditions detected or diagnosed after study treatment administration even though it may have been present prior to the start of the study
- Signs, symptoms, or the clinical sequelae of a suspected interaction
- Signs, symptoms, or the clinical sequelae of a suspected overdose of either study treatment or a concomitant medication (overdose per se will not be reported as an AE/SAE) unless this is an intentional overdose taken with possible suicidal/self-harming intent. This should be reported regardless of sequelae

"Lack of efficacy" or "failure of expected pharmacological action" per se will not be reported as an AE or SAE. However, the signs and symptoms and/or clinical sequelae resulting from lack of efficacy will be reported if they fulfill the definition of an AE or SAE

Events that **do not** meet the definition of an AE include:

- Medical or surgical procedure (e.g., endoscopy, appendectomy); the condition that leads to the procedure is an AE
- Situations where an untoward medical occurrence did not occur (social and/or convenience admission to a hospital)
- Anticipated day-to-day fluctuations of pre-existing disease(s) or condition(s) present or detected at the start of the study that do not worsen
- The disease/disorder being studied, or expected progression, signs, or symptoms of the disease/disorder being studied, unless more severe than expected for the subject's condition

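### Section 2.8.2 compares adverse events only as an any-grade proportion and an any-grade count, although Aim 2 names severity and the grades are collected

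*Combined protocol and SAP*

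**What the plan says.** The synopsis, under Specific Aim 2, lists among the secondary endpoints "the rate and severity of adverse events (AE) at any time during treatment". Section 1.2 refers only to adverse events, and section 2.7.2 lists the third secondary endpoint as "Adverse event comparisons", without naming severity. Section 2.7.2 then says: "The NCI Common Toxicity Criteria Scale will be used to define grades (severity) of adverse events and toxicities". Section 5.6.2 sets out grades 1 to 5.

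Section 2.9.2 gives the expected safety result: "we anticipate high-grade adverse events will not be significantly more frequent among experimental arm subjects".

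The analysis is one sentence in section 2.8.2: "The proportion of subjects with adverse events and the count of adverse events per subject will be compared by treatment". The proportion gets a Fisher exact test and the count an exact Poisson test. The sentence sets no grade or seriousness threshold.

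Two other places touch on serious events. Section 5.6.3 lists AEs of special interest whose frequency is to be assessed in the analyses and final report. Section 5.6.4 bases the study-wide stopping rule on comparing serious AE (SAE) rates between the arms, with no test or threshold.

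**The concern.** Severity is part of a stated secondary endpoint and the basis of the stated safety expectation. It is recorded for every event, and then enters no planned analysis. A grade 1 headache and a grade 4 infection each make the subject a case in the proportion, and each add one to the count. The expectation in section 2.9.2 about high-grade events therefore has no analysis that could bear it out or contradict it.

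The any-AE proportion has a further weakness. The definition in section 5.6.1 is broad: "An AE can therefore be any unfavorable and unintended sign (including an abnormal laboratory finding), symptom, or disease (new or exacerbated) temporally associated". Table 2 and its notes give 19 contacts after screening (9 visits from day 1 to day 210, 8 next-day calls, and contacts at days 240 and 300). If most placebo subjects report something over that period, the proportion is near its ceiling in both arms. A non-significant result would then carry little information about harm and none about severity.

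**Working it through.** **1. Endpoint against analysis.**

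| Element | Where named | Analysis by arm |
|---|---|---|
| AE rate | Synopsis Aim 2; 2.7.2 | 2.8.2: proportion (Fisher), count (exact Poisson) |
| AE severity (grade) | Synopsis Aim 2; expectation in 2.9.2 | none |
| Special-interest events | 5.6.3 | frequency; no comparison named |
| SAEs | 5.6.4 | rates compared for the stopping rule; no test, threshold or grade |

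**2. The plan's own figure.** Section 2.8.1 gives power 0.8 for the primary endpoint (12 vs 6, difference 30%, SD 20%, alpha 0.05). The noncentrality is 30 / (20 × √(1/12 + 1/6)) = 3.0 on 16 df, so a two-sided t test has power 0.804. The figure is reproduced, but it says nothing about AEs. The documents give no power or expected any-AE rate for the AE comparison. The steps below assume two-sided alpha 0.05.

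**3. Fisher's test on the any-AE proportion, 12:6.** Take the extreme case in which all 12 belimumab subjects have an AE. If m placebo subjects have none, this table has probability C(6,m) / C(18,m). For m = 0 it is the only possible table. For m = 1 to 3 it is the least likely table, so this is the two-sided p.

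- 6/6 placebo with an AE: p = 1.00
- 5/6: 6/18 = 0.33
- 4/6: 15/153 = 0.098
- 3/6: 20/816 = 0.025

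So p ≤ 0.05 requires at most 3 of 6 placebo subjects with an AE.

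**4. How likely that is.** With X ~ Binomial(6, π), where π is an assumed placebo any-AE risk:

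| Assumed π | 12:6, P(X ≤ 3) | 17:8, P(X ≤ 5) |
|---|---|---|
| 50% | 0.66 | 0.86 |
| 70% | 0.26 | 0.45 |
| 80% | 0.10 | 0.20 |
| 90% | 0.016 | 0.038 |

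The 17:8 column assumes that split of the 25 randomised subjects. There, 5/8 gives p = 56/2300 = 0.024 and 6/8 gives 28/300 = 0.093. These probabilities are the power when the belimumab risk is 100%. At a belimumab risk of 95%, the 12:6 figures for π = 70%, 80% and 90% fall to 0.16, 0.06 and 0.009.

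**5. The count per subject.** This has no ceiling. Simulated power of the exact Poisson comparison at 12:6, for a rate ratio of 2, is 0.60 at an assumed 2 AEs per placebo subject and 0.89 at an assumed 4. These figures assume pure Poisson variation. Every event still counts as one, whatever its grade.

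**6. What a grade-based comparison can deliver.** With 0/6 placebo subjects having a grade 3 or higher AE, Fisher's test gives p = 0.054 at 6/12 and 0.038 at 7/12, so 7 of 12 are needed. At assumed risks of 10% vs 30% the power is 0.02, and at 10% vs 50% it is 0.23. A test is therefore of little use, but an interval is informative. For 0/12, the exact 95% upper limit is 1 − 0.025^(1/12) = 26%. For 0/6, it is 1 − 0.025^(1/6) = 46%.

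**The case against.** A reader might infer that the whole planned AE comparison saturates and can hardly show harm. The documents do not support that. Only the proportion has a ceiling, and the count has reasonable power for a doubled rate (step 5).

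A reader might also take it as given that nearly every subject will have an AE. The documents state no any-AE rate, and they narrow the definition. Section 5.6.1 leaves out anticipated day-to-day fluctuation and expected manifestations of the disease under study. Section 5.6.2 records laboratory abnormalities only if judged clinically significant. The synopsis excludes recent or frequent exacerbators. At a 50% placebo risk the Fisher test could still have power of up to 0.66. A high rate is plausible, but it remains an assumption.

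Nor is severity the whole safety endpoint: Aim 2 names rate as well, and section 2.8.2 does address rate. Serious events are not ignored either, since sections 5.6.3 and 5.6.4 deal with them in part. Seriousness is not grade, however: section 5.6.2 defines the two separately, and neither place yields a by-arm summary by severity.

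Finally, a grade 3 or higher comparison is itself weak in 18 subjects. That is correct, and the protocol admits limited power in sections 2.8.1 and 2.9.1. It argues for estimation in place of a test. It does not argue for leaving severity out.

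**Conclusion.** The gap stands and rests on the text alone: severity is named in the synopsis Aim 2, graded under sections 2.7.2 and 5.6.2, and relied on in section 2.9.2, but no planned between-arm analysis uses grade. The special-interest frequencies and the SAE comparison for stopping fill it only in part.

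The weakness of the any-AE proportion is conditional. Even with 12/12 belimumab subjects affected, significance needs 3/6 or fewer placebo subjects affected. The chance of that is 26%, 10% or 1.6% at assumed placebo risks of 70%, 80% or 90%. It does not extend to the count, whose limitation is equal weighting of all grades.

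**What to change.** In section 2.8.2, and in the definition of secondary endpoint 3 in section 2.7.2:

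- Add a by-arm table of each subject's worst CTCAE grade, citing version 4.0 as section 2.6 does, with a row for no AE.
- Add the proportions of subjects with at least one grade 3 or higher AE and with at least one SAE. Give exact confidence intervals for each arm and for the difference, labelled as estimation.
- Keep the any-AE proportion and the count. State that a non-significant any-AE test is not evidence on severity.

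A rank test on worst grade is optional.

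The cost is wording, since the grades are already to be collected. The downside is that the intervals will be wide, as the limits in step 6 show. They will not establish that high-grade events are no more frequent on belimumab, but they will show how large an excess the data leave open.
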